## **GUIDANCE ON TOXICITY MANAGEMENT FOR SPECIFIED TOXICITIES:**

### **Guidance for Injection Site Reactions (ISRs)**

The CMC must be informed of all Grade 3 or 4 ISRs to determine etiology and assess appropriate continued study participation. ISR discomfort can be managed symptomatically (e.g. cold/warm compress, acetaminophen, ibuprofen) if the reaction is interfering with the participant's ability to perform activities of daily living.

### **Guidance for Allergic Reactions**

Participants may continue to receive oral or injectable study product for Grade 1 or 2 allergic reactions at the discretion of the IoR or designee. The participant should be advised to contact the study site staff immediately if there is any worsening of symptoms or if further systemic signs or symptoms develop. Antihistamines, topical corticosteroids, or antipruritic agents may be prescribed.

Participants with Grade  $\geq 3$  allergic reactions that are considered to be related to study product should permanently discontinue study product and continue to be followed quarterly. Participants should be treated as clinically appropriate and followed until resolution of the AE.

1. LIST OF ABBREVIATIONS AND ACRONYMS

Term/Abbreviation	Definition
ADaM	Analysis Dataset Model
AEs	Adverse Events
AESI	AEs of Special Interest
ALT	Alanine Aminotransferase
AST	Aspartate Aminotransferase
CAB LA	Long-Acting Cabotegravir
CABG	Coronary Artery Bypass Grafting
CASI	Computer Assisted Self Interview
CBC	Complete Blood Count
CMC	Clinical Management Committee
CPK	Creatine Phosphokinase
CRF	Case Report Forms
CV	Coefficient of Variation
DAIDS	Division of AIDS
EC	Ethics Committee
FDA	(US) Food and Drug Administration
GEE	Generalized Estimating Equations
HBsAg	Hepatitis B Virus Surface Antigen
HBV	Hepatitis B Virus
HDL	High Density Lipoprotein
IM	Intramuscular
IoR	Investigator of Record
IRB	Institutional Review Board
ISR	Injection Site Reaction
IUS	Intrauterine System
LDL	Low Density Lipoprotein
MO	Medical Officer
NIAID	National Institute of Allergy and Infectious Diseases
NICHD	National Institute of Child Health and Human Development
OHRP	Office for Human Research Protections
PTCA	Percutaneous Transluminal Coronary Angioplasty

SD	Standard Deviation
SMC	Safety Monitoring Committee
SPDSMP	Study Progress and Data Safety Monitoring Plan
STI	Sexually Transmitted Infection
Tbili	Total Bilirubin
ULN	Upper Limit of Normal
US	United States
WBC	White Blood Cell
WHO	World Health Organization

Approved

2. INTRODUCTION

This SAP is intended to describe the final primary and secondary analyses upon completion of HPTN083-01. Sections of the SCHARP SAP template had to be adapted here to reflect the distinct single-arm outcomes, as opposed to the more common multi-arm studies that the template was designed for. Key variable definitions are included in Appendix B.

2.1 General Design Considerations

HPTN083-01 is a phase IIB single arm trial designed to establish the minimum safety, tolerability and acceptability data needed to support the use of cabotegravir long-acting injection (CAB LA) in an adolescent population, potentially transforming the field of HIV prevention for young people. The study target population is sexually active, healthy male adolescents aged below 18 years. The study target is to enroll more than 50 participants with at least 50 participants receiving at least one injection. Participant recruitment will take approximately 12 months.

Study participation includes Step 1: a 5-week oral CAB 30mg QD safety lead-in followed by Step 2: a series of 5 intramuscular (IM) injections of 3 mL (600 mg) cabotegravir administered at 8-week intervals after a 4-week loading dose (injections at weeks 5, 9, 17, 25 & 33). Adherence support strategies (e.g., counseling, reminders, pill cases) will be included to support pill-taking during the first five weeks and to support retention during the injectable phase. A safety visit will follow each injection to ascertain pharmacokinetic-peak safety data, including injection site reactions. Step 3: A blood draw visit, the +8 Week Visit, will follow the week 33 injection to monitor CAB drug levels. All participants who have received at least one injection will be followed for 48 weeks after their last injection. Waning levels of cabotegravir (the PK tail) will be covered with locally sourced oral TENOFOVIR/EMTRICITABINE (TRADE NAME: TDF/FTC, TRUVADA®) for daily use for 48 weeks. In Step 3 participants may also choose to continue with 8-week dosing of injectable of CAB-LA for 48 weeks (5 additional injections beyond the initial 5 injections, administered at weeks +8, +16, 24, +32, +40, and +48.) Behavioral and acceptability data will be collected via computer-assisted self-interview (CASI). Total participant commitment for the entire study is up to 87 weeks, or approximately 1.5 years. We anticipate recruitment for the study will take approximately 12 months.

Participants who discontinue study product during Step 2 for any reason other than HIV infection or AE occurrence will be transitioned to open label TDF-FTC for 48 weeks.

There are in total three study sites:

- Adolescent and Young Adult Research at the Core Center (AYAR at CORE), Chicago, IL;
- St. Jude Children's Research Hospital CRS, Memphis, TN;
- Fenway Health CRS, Boston, MA.

2.2 Study Objectives and Endpoints

Primary objectives:

- To evaluate the safety, tolerability, and acceptability of CAB LA in healthy, HIV-uninfected male adolescents aged below 18 years.

Secondary objectives:

- To examine adherence to and timeliness of injections over time among adolescent participants provided CAB LA and information regarding its safety and efficacy.
- To examine patterns of sexual risk behavior over time among adolescent participants provided CAB LA and information regarding its safety and efficacy.
- To evaluate the safety of oral CAB during step 1 (oral phase) as well as all study products during the aggregate oral+injectable period for all enrolled participants. Additionally, we will include an intention to treat analysis for the primary safety endpoint.
- To characterize the pharmacokinetics of CAB LA
- Additional exploratory analyses will be done with the laboratory and clinical data, including resistance mutations

To achieve the primary and secondary objective, the planned primary and secondary endpoints are:

Primary endpoints:

Safety endpoint: Proportion of participants experiencing any Grade 2 or higher clinical adverse events (AEs) and laboratory abnormalities among participants who receive at least one injection of CAB LA. Laboratory abnormalities include grade 2 or above on tests include (CRF: Chemistry Panel, Fasting Lipid Test Results, Urinalysis, Hematology):

- Renal function: Creatinine, Creatinine clearance
- Hematology: Hemoglobin, Platelets, WBC, Neutrophils, Lymphocytes
- Liver function: Alkaline phosphatase, AST, ALT, Total bilirubin
- Electrolytes: Phosphorus, Calcium
- Other chemistries: CPK, Glucose, Amylase, Lipase,
- Urine test: Protein, Glucose
- Fasting Lipid Test Results: Total cholesterol, Triglycerides, LDL, HDL

Tolerability endpoint: Proportion of participants who receive at least 1 injection and who discontinue receiving injections prior to the full course of injections due to intolerance of injection, frequency of injections or burden of study procedures. Reasons for intolerance may include:

- Injection site reaction
- Participant refused further participation¹
- Participant lost to follow-up
- Participant is unwilling or unable to comply with required study procedures
- Participant refused further study product use
- Participant unable to adhere to visit schedule

¹Excluding cases in which reason for termination is unrelated to intolerance

Acceptability endpoints: Proportion of participants who complete all scheduled injections and proportion of participants who receive at least one injection who would consider using CAB LA for HIV prevention in the future. This endpoint will be evaluated using CASI questionnaires at the last injection visit (Step 2, week 33) for participants who do not have acceptability data at the Step 2, week 33 visit (either due to a change in when the questionnaire items were administered², missed the final injection visit, or discontinue injections early) and continue to step 3, acceptability endpoints are evaluated during the follow up phase (step 3, week +12). The primary acceptability outcome is:

If you wanted to protect yourself from getting HIV, which of the following product(s) would you prefer to use?

- Prefer not using a product
- Condoms only
- Oral PrEP pills only
- Injectable PrEP only
- Condoms and oral PrEP pills together
- Condoms and injectable PrEP together
- Prefer not to answer

Secondary endpoints:

- Proportion of injection visits that occurred “on-time”
 - The target visit window for the week 5 injection is 0-3 days after the Week 5 visit date (allowing for the injection occurring on a different day from the W5 visit) and is +/-3 days from the target injection date for all other injection visits. Visits happening within the target window are considered “on-time”
- Change from enrollment of self-reported sexual behavior (number of sexual partners, increased episodes of anal sex without a condom) during the study period
- Proportion of participants experiencing Grade 2 or higher clinical AEs and laboratory abnormalities in the oral phase and the aggregate over the entire study period
- Plasma CAB pharmacokinetics

2.3 Randomization

There is no treatment randomization as this study is a single arm, open label trial.

2.4 Blinding

Participants and site staff will be unblinded throughout the trial.

2.5 Sample Size and Power

The sample size for this protocol (n=50) is the number of participants agreed upon by the industry sponsor and regulators in order to provide supplementary safety and behavioral data on adolescents in collaboration with the HPTN 083 and HPTN 084 adult trials. The goal of the safety evaluation for this study is to identify safety concerns associated with CAB LA.

Table 2. Width of 95% confidence interval for estimated proportion as a function of the true proportion, assuming a sample size of 50.

True proportion	Width of 95% CI
0.1	± 0.083
0.2	± 0.11
0.3	± 0.13
0.4	± 0.14
0.5	± 0.14

Since each of the primary endpoints is a proportion, Table 2 shows the precision (confidence interval width) that will be obtained for each endpoint with a sample size of 50.

Recognizing that some participants will not reach the first injection visit and/or may not receive any study injections due to personal or clinical concerns, the study will continue to recruit participants until it is clear that at least 50 participants will progress to the injection phase. Experience in the parent study HPTN 083 suggests that only a small proportion of participants will fail to reach the injection stage, and it is expected that approximately 5-7 additional enrollees may be needed in order to reach 50 participants in the injection phase.

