### 7.3 Sample Size

The sample size for this protocol (n=50) is the number of participants agreed upon by the industry sponsor and regulators in order to provide supplementary safety and behavioral data on adolescents in collaboration with the HPTN 083 and HPTN 084 adult trials. The goal of the safety evaluation for this study is to identify safety concerns associated with CAB LA.

Since each of the primary endpoints is a proportion, Table S1 shows the precision (confidence interval width) that will be obtained for each endpoint with a sample size of 50.

Table S1. Width of 95% confidence interval for estimated proportion as a function of the true proportion, assuming a sample size of 50.	
True proportion	Width of 95% CI
0.1	± 0.083
0.2	± 0.11
0.3	± 0.13
0.4	± 0.14
0.5	± 0.14

The study will recruit sufficient participants to ensure that at least 50 participants progress to the injection phase.

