### **7.7.1 Safety Endpoints**

The primary safety analysis will include Grade 2 or higher clinical and laboratory events that occur from the initial injection to 48 weeks after the last injection among participants who receive at least one injection.

To assess safety, the number and the percent of participants experiencing each safety endpoint will be tabulated. Each participant will contribute once in each category (for example, only for the highest severity AE for each participant) for the calculation of event rates. Exact binomial confidence intervals will be calculated for each safety endpoint.

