### **7.7.4 Tolerability**

To assess tolerability, the number and the percent of participants who receive at least one injection and discontinue receiving injections prior to the full course due to intolerability of injection (including but not limited to ISR), frequency of injections, or burden of procedures or any AE will be tabulated.

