5. GENERAL ANALYSIS METHODS

[figure not shown]
Within the single arm, all primary and secondary outcome proportions with 95% CIs will be calculated.

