8. PRIMARY ANALYSES

For each of the three primary endpoints the number and proportion of participants will be computed along with corresponding 95% confidence intervals. Each summary will be provided both overall and by site. Endpoint descriptions are available in section 2.2.

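### The stated precision is a normal-approximation half-width at n=50, although the protocol plans exact intervals for safety, the SAP names no interval method, and enrollment stopped at nine

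*SAP*

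**What the plan says.** SAP 2.5 heads its Table 2 "Width of 95% confidence interval for estimated proportion as a function of the true proportion, assuming a sample size of 50" and lists ±0.083, ±0.11, ±0.13, ±0.14 and ±0.14 for true proportions 0.1 to 0.5. It states that "Table 2 shows the precision (confidence interval width) that will be obtained for each endpoint with a sample size of 50". Protocol 7.3 prints the same values and says that "Table S1 shows the precision (confidence interval width) that will be obtained for each endpoint with a sample size of 50". Neither gives a formula.

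On the interval to be reported, protocol 7.7.1 is explicit for safety: "Exact binomial confidence intervals will be calculated for each safety endpoint". For tolerability, protocol 7.7.4 plans only a count and percentage of participants who stop injections for reasons that include "frequency of injections, or burden of procedures or any AE will be tabulated"; no interval is mentioned. Protocol 7.7.5 does the same for acceptability.

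The SAP widens the requirement but drops the method. SAP 5 says "Within the single arm, all primary and secondary outcome proportions with 95% CIs will be calculated". SAP 8 says that for each of the three primary endpoints "the number and proportion of participants will be computed along with corresponding 95% confidence intervals". SAP 6.4 reports that enrollment was stopped in January 2022 after nine participants.

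**The concern.** There are three gaps.

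- For the safety endpoints, the precision that the table promises is not the precision that the protocol's own method gives.
- For tolerability and acceptability, the SAP requires an interval and no document says which one.
- The SAP reports the stop at nine, yet its only precision statement is still for 50.

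With 50 participants this would matter little. With nine or fewer, the choice of method decides the reported interval, most of all when the count is at or near zero (stops for intolerance) or at or near the maximum (completion of all injections). If the method is left open, it can be chosen after the counts are known. For a safety or tolerability proportion the upper limit is what a reader uses.

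**Working it through.** **Inputs.** n=50 and the five ± values (SAP 2.5, protocol 7.3); 95% two-sided intervals (SAP 8); nine enrolled (SAP 6.4). The safety and tolerability analyses use the Injection population (SAP 8.1, 8.2). Its size is not stated, so nine is an upper bound; 5 to 8 is used below as an assumed range.

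**1. Reproduce the table.** Wald half-width = 1.96 × √(p(1−p)/n). For p=0.1: 1.96 × √(0.09/50) = 0.0832. All five rows match at the printed rounding. Continuity-corrected Wald, Wilson and exact intervals do not reproduce the column. The values are half-widths, although the column is labelled as width.

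**2. Exact interval at n=50.** The Clopper-Pearson limits for x events are the 0.025 quantile of Beta(x, n−x+1) and the 0.975 quantile of Beta(x+1, n−x). Setting x = 50p:

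| p | Stated | Wald | Exact limits | Exact half-width | Lower / upper arm |
|---|---|---|---|---|---|
| 0.1 | ±0.083 | 0.0832 | 0.033 to 0.218 | 0.092 | 0.067 / 0.118 |
| 0.2 | ±0.11 | 0.1109 | 0.100 to 0.337 | 0.118 | 0.100 / 0.137 |
| 0.3 | ±0.13 | 0.1270 | 0.179 to 0.446 | 0.134 | 0.121 / 0.146 |
| 0.4 | ±0.14 | 0.1358 | 0.264 to 0.548 | 0.142 | 0.136 / 0.148 |
| 0.5 | ±0.14 | 0.1386 | 0.355 to 0.645 | 0.145 | 0.145 / 0.145 |

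The exact half-width exceeds the Wald one by 0.006 to 0.009. The asymmetry is clear only at low proportions; by symmetry it reverses above 0.5.

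**3. Actual size.** By the table's own formula, going from 50 to 9 multiplies the half-width by √(50/9) = 2.36; at p=0.1 it becomes 0.196. The two methods at n=9 give:

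| Events | Wald | Exact |
|---|---|---|
| 0/9 | 0 to 0 | 0 to 0.336 |
| 1/9 | −0.094 to 0.316 | 0.003 to 0.482 |
| 2/9 | −0.049 to 0.494 | 0.028 to 0.600 |
| 9/9 | 1 to 1 | 0.664 to 1 |

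With no events the exact upper limit is 1 − 0.025^(1/n). It is 0.336 for n=9, and 0.369, 0.410, 0.459 and 0.522 for n = 8, 7, 6 and 5.

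**4. Coverage if Wald were used at n=9.** At a true rate of 0.10, Wald misses when x=0 (probability 0.387) and when x≥4 (0.008), so coverage is 1 − 0.387 − 0.008 = 0.60 rather than 0.95. At 0.05 it is 0.37 and at 0.20 it is 0.85. Exact coverage at these three rates is at least 0.98.

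**The case against.** The best defence is that nothing is miscalculated. The table matches its formula, is conditional on n=50, and did not drive the design, because both documents say the number was agreed with the industry sponsor and regulators. Protocol 7.7.1 already fixes the exact method for safety; the SAP is silent there and does not contradict it. All of that stands. The point is a specification gap and an out-of-date precision statement.

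Four stronger readings are tempting, and the documents do not support them.

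- *The analysis will use Wald intervals.* No document says so. Table 2 is a planning table, and the coverage figures above show only what would follow if its method were carried over.
- *The n=50 precision is badly understated.* At 5/50 the upper arm is 0.118 against 0.083, about 42% longer, but that is the worst row and one arm only. The lower arm there is shorter than stated, and the half-width differs by 0.009 at most.
- *Zero or one tolerability stop is to be expected.* No rate is given for this trial. Adult figures quoted in the protocol are 2/134 stops for injection site reactions (1.5%) and 4 of 94 withdrawals citing injection tolerability (4.3%), but this trial's definition is broader. If any-reason non-completion among those injected is taken from the protocol's HPTN 077 figures, 1 − 75/89 = 16%, the chance of 0 or 1 in nine is about 0.57.
- *By-site results should be deleted because they expose minors.* SAP 8 does say "Each summary will be provided both overall and by site", and nine participants at three sites is few. But the split by site is not given, nothing says such tables will be published, and SAP 12 restricts secondary results to overall summaries only for the clinical study report. This point does not rest on it.

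**Conclusion.** The point holds as a gap that should be closed. The stated precision is a Wald half-width, which is not what the protocol's planned exact interval gives, and it refers to a sample size that the same SAP says was not reached. At n=50 the error is 0.006 to 0.009 in half-width and of little consequence. At nine or fewer it matters: an exact upper limit of 0.336 for 0/9, rising to 0.52 if only five were injected, and 0.482 for 1/9. The method for tolerability and acceptability is fixed nowhere, although SAP 5 and 8 require an interval for both. The size of the problem rests on two assumptions: that between five and nine were injected, and, for the coverage figures, that Wald might be used.

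**What to change.** 1. In SAP 2.5, replace the ± column of Table 2 with exact lower and upper limits, at n=50 (as in step 2 above) and at the number actually injected. Completion of injections is also reported in the Enrolled population (SAP 8.3.1), where the n=9 limits apply.
2. In SAP 5 and 8, state that two-sided Clopper-Pearson 95% intervals are used for all three primary endpoints and for binary secondary endpoints counted per participant. The on-time proportion in SAP 12.4 counts several injections per participant, so it is not covered by this wording.

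The cost is two sentences and one recalculated table. The downside is that the stated precision becomes less favourable: slightly at n=50, and markedly at the actual size.

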3. GENERAL DATA ANALYSIS CONSIDERATIONS

3.1 Analysis Set(s)

Primary and secondary analyses will be carried out among the following populations:

Screened Population: Includes all participants who were screened for potential enrollment.

Injection Population: Includes enrolled participants who receive at least one injection of CAB LA.

Safety Population: Includes enrolled participants who began step 1 (oral phase).

Enrolled Population: Includes all enrolled participants.

Seroconverter Population: Includes all enrolled participants who seroconverted during the study.

TDF/FTC Population: All enrolled participants who were provided TDF/FTC during the study.

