6. TRIAL PARTICIPANT DISPOSITION

6.1 Disposition of Participants

The study will recruit participants to ensure that at least 50 participants progress to the injection phase, therefore more than 50 participants will be screened and enrolled.

Consort Diagram

¹Conditions in Step 1 that could disqualify a participant from transitioning to Step 2 are as follows:

- Pill count suggestive of less than 50% adherence at the Week 4 visit
- Missed or delayed Week 4 visit
- Grade 2 ALT at week 4, or grade 3 and above ALT anytime in step 1
- Grade 3 AE that is related to study product anytime in step 1, excluding ALT & CPK
- Grade 4 AE anytime in step 1, excluding ALT & CPK
- Grade 3 and above CPK and < Grade 3 ALT
- At substantial risk of HIV infection and/or qualifies for oral PrEP by local guidelines
- Any HIV reactive/positive test

Participant enrollment inclusion and exclusion criteria (see study protocol)

A. Inclusion Criteria

- 1) Assigned male at birth (including MSM, TGW, and gender non-conforming people)
- 2) At enrollment, below 18 years of age
- 3) At enrollment, body weight ≥ 35 kg (77 lbs.)
- 4) Willing to provide written informed assent/consent for the study and/or able to obtain written parental/guardian informed consent
- 5) Self-reported sexual activity with a male in the past 12 months
- 6) In general, good health, as evidenced by the following laboratory values:
 - a. Non-reactive / negative HIV test results
 - b. Absolute neutrophil count > 799 cells/mm³
 - c. Platelet count $\geq 100,000$ /mm³
 - d. Hemoglobin > 11 g/dL
 - e. Calculated creatinine clearance ≥ 60 mL/minute using the modified Schwartz equation (\leq grade 2)
 - f. Alanine aminotransferase (ALT) < 2.0 times the upper limit of normal (ULN) and total bilirubin (Tbili) $\leq 2.5 \times$ ULN
 - g. Hepatitis B virus (HBV) surface antigen (HBsAg) negative and accepts vaccination
 - h. HCV Antibody negative
- 7) Willing to undergo all required study procedures
- 8) If currently on PrEP from a non-study source, willing to stop said PrEP prior to enrollment and agree to switch to oral CAB for the lead-in period and CAB LA injections.

B. Exclusion Criteria

- 1) Co-enrollment in any other HIV interventional research study or other concurrent studies which may interfere with this study (as provided by self-report or other available documentation);
- 2) Past or current participation in HIV vaccine trial with exception for participants who can provide documentation of receipt of placebo;

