6.4 Unplanned enrollment discontinuation

In January 2022 the HPTN leadership determined that the study accrual rate was insufficient to meet the target enrollment in a reasonable amount of time, and study enrollments were stopped after a total accrual of nine participants.

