8.3 Acceptability endpoint analysis

8.3.1 Completion of scheduled injections

Population: Injection population and Enrolled population

Analysis description: Number and percent of participants who complete all scheduled injections¹

¹Definition of completing all scheduled injections for participants who are confirmed HIV positive or discontinue product due to the following reasons:

- Death
- Early study closure
- HBV infection

During Step 1:

Enrolled population: completed all 0 of 0 scheduled injections

Injection population: not applicable, did not receive injection

During Step 2:

Both enrolled and injection populations: completed all injections whose target window closed prior to death/seroconversion/product discontinuation date

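### SAP v2.0 still plans for at least 50 injected participants and gives precision only for n=50, although its own Section 6.4 records that enrollment stopped at nine

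*SAP*

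**What the plan says.** SAP Section 2.5 sets the sample size at 50 and commits to it in the future tense: "the study will continue to recruit participants until it is clear that at least 50 participants will progress to the injection phase". It expects that "approximately 5-7 additional enrollees may be needed in order to reach 50 participants in the injection phase". It then states that "Table 2 shows the precision (confidence interval width) that will be obtained for each endpoint with a sample size of 50". No other sample size is tabulated.

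Section 2.1 gives the same aim as a target: "The study target is to enroll more than 50 participants with at least 50 participants receiving at least one injection". Section 6.1 states it as a commitment: "The study will recruit participants to ensure that at least 50 participants progress to the injection phase".

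Section 6.4 dates the decision on slow accrual to January 2022 and says that "study enrollments were stopped after a total accrual of nine participants". The change history makes version 2.0 effective at the last signature, and the signatures shown are dated 17 January 2023. It also lists Sections 2 and 6 among those revised for that version.

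The Injection population is defined in Section 3.1: "Includes enrolled participants who receive at least one injection of CAB LA". Safety (8.1), tolerability (8.2) and product preference (8.3.2) use that population alone. Completion of injections (8.3.1) is the exception: "Population: Injection population and Enrolled population".

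On method, SAP Sections 5 and 8 ask for 95% confidence intervals without naming one. Protocol 7.7.1 specifies exact binomial intervals for the safety endpoints. For tolerability and acceptability neither document names a method.

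**The concern.** The same signed document says both that recruitment will go on to at least 50 injected participants and that it ended about a year earlier at nine enrolled. A reader who goes to Section 2.5 to learn how precisely the primary proportions will be known gets figures for a size that was never reached, with no pointer to the section that says so.

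This matters because Section 2.5 gives the aim of the safety evaluation as finding safety concerns, and it is the only place where the SAP states precision. With at most nine injected, seeing no events still leaves room for a true rate of about one in three. At this size the interval method also changes the reported result, so leaving it unnamed has consequences that it would not have at n=50.

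**Working it through.** **Inputs.** Planned n = 50, and true proportions 0.1 to 0.5 (SAP 2.5, Table 2). Enrolled = 9 (SAP 6.4). The number injected is not stated in the text, so nine is an upper bound and 7 to 9 is shown as an assumption. Section 2.5's own allowance of 5 to 7 extra enrollees per 50 injected supports that range: 9 × 50/57 = 7.9 and 9 × 50/55 = 8.2.

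**Reproducing Table 2.** Half-width = 1.96 × √(p(1−p)/n). At n = 50 this gives 0.083, 0.111, 0.127, 0.136 and 0.139 for p = 0.1 to 0.5. These match all five stated values after rounding, so Table 2 uses the normal approximation and is correct for its stated n.

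**The same formula at the attainable sizes.**

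| n | Half-width, p = 0.1 to 0.5 | Ratio to n = 50 |
|---|---|---|
| 9 | 0.196, 0.261, 0.299, 0.320, 0.327 | √(50/9) = 2.36 |
| 8 | 0.208 to 0.346 | √(50/8) = 2.50 |
| 7 | 0.222 to 0.370 | √(50/7) = 2.67 |

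**Exact (Clopper-Pearson) 95% limits.** The upper limit after zero events is 1 − 0.025^(1/n). Limits for one event come from beta quantiles.

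| n | Zero events, upper limit | One event |
|---|---|---|
| 50 | 7.1% | – |
| 9 | 33.6% | 0.3% to 48.2% |
| 8 | 36.9% | 0.3% to 52.7% |
| 7 | 41.0% | 0.4% to 57.9% |

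**Chance of seeing at least one event,** 1 − (1−p)^n.

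| True risk | n = 50 | n = 9 | n = 8 | n = 7 |
|---|---|---|---|---|
| 5% | 92% | 37% | 34% | 30% |
| 10% | 99.5% | 61% | 57% | 52% |

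**Does the method matter at nine?** For 1/9 the normal approximation gives 0.111 ± 1.96 × √(0.111 × 0.889/9) = 0.111 ± 0.205, or −9.4% to 31.6%. The exact interval is 0.3% to 48.2%. For 0/9 the approximation has zero width, while the exact upper limit is 33.6%.

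**The case against.** The best defence is that nothing is hidden. Section 6.4 has its own heading, gives the date, reason and count of the stop, and sits in the same Section 6 as 6.1. Table 2 says that it assumes 50, and the statement that 50 was agreed with the sponsor and regulators remains true as history. Sections 5 and 8 already require intervals on every primary proportion, and these will show their own width when computed. With enrollment closed, a new precision table cannot alter the trial. These points limit the weight of the finding. They leave two sections that contradict 6.4 without any label, and an SAP that gives no precision for the study it will analyse.

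The scale can also be challenged. The ratio of 2.36 belongs to Table 2's formula. Expected exact half-widths at n = 9 are 0.224, 0.264, 0.291, 0.307 and 0.312, against 0.090, 0.117, 0.132, 0.141 and 0.143 at n = 50, so the ratio is about 2.2 to 2.5. Detection is also much better for common events: at n = 9 it is 87% for a true risk of 20% and 96% for 30%, and the primary safety endpoint covers any Grade 2 or higher event across a long laboratory list. Both points are fair. The loss is greatest for uncommon events.

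On method, the protocol's exact intervals already cover safety, and extending them to tolerability and acceptability goes beyond its wording. That is so, but the comparison at 1/9 and 0/9 shows why one method should be named for all the primary proportions. Two graphics could not be read: the CONSORT diagram in 6.1 and an item just before the interval sentence in Section 5. If either carries a count or a method, that should be used.

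**Conclusion.** The concern stands. As signed, Sections 2.5 and 6.1 state a sample size that Section 6.4 had already ruled out, and the only precision given belongs to that size. Section 2.1 is milder because it states a target.

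At best (all nine injected) the intervals are about 2.4 times as wide as Table 2 indicates by its own formula, and the zero-event upper limit is nearly five times as high (33.6/7.1 = 4.7). If only seven or eight were injected, both are worse. The count of nine comes from the SAP; the range of 7 to 9 injected is an assumption.

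The consequence is for interpretation only: no test, decision threshold, endpoint or population depends on Table 2. The text should be corrected, but the planned analyses remain valid. The unnamed interval method is a smaller gap.

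**What to change.** - In Sections 2.5 and 6.1, keep Table 2 and the statements about 50 participants, but label them as the original plan, superseded by Section 6.4, with a cross-reference.
- Beside Table 2, add a short table of exact (Clopper-Pearson) 95% intervals for the number actually in the Injection population, including the upper limit for zero events. State that number, and note that the Enrolled population used in 8.3.1 is nine.
- In Sections 5 and 8, name the exact binomial method for the primary proportions. This carries over what Protocol 7.7.1 says for safety and extends it to tolerability and acceptability.

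The cost is a cross-reference in two sections, one small table and one sentence on method.
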